#### **1.4 Rationale for the Study**

Equivalent effects on HbA1c and greater weight loss effects were observed for OPK-88003 compared to exenatide ER in the phase 2 trial XNAA. These findings are consistent with the hypothesis that the additional glucagon activity associated with OPK-88003 provides equivalent glycemic control and superior weight loss compared to GLP-1 modulation alone. Since it has been demonstrated that additional weight loss can be obtained by increasing the dose of GLP-1 agonists ([Davies et al 2015](#)), it seems likely that increasing the dose of OPK-88003 will demonstrate additional weight loss benefits.

XNAA investigated the dose-response relationship of OPK-88003 versus placebo and positive control exenatide ER, and established that QW injections over 24 weeks could reduce HbA1c by up to 1.43% and weight by up to 3.3 kg. The severity of the OPK-88003 AE profile observed so far, including the 50 mg QW dose tested in the phase 2 trial, does not outweigh the anticipated favorable benefits on glucose and body weight. Thus, the benefit-risk balance of OPK-88003 supports additional clinical testing of OPK-88003 at doses higher than 50 mg QW.

There was also a dose-dependent increase in GI side effects with higher OPK-88003 doses in prior human studies, however, these effects were transient in nature. In efforts to optimize OPK-88003 for glucose control and body weight reduction, it is likely that dose escalation could be key for reducing GI side effects through gradual up-titration of doses to target dose levels. Other GLP-1 agonists, such as liraglutide QD (once daily) and semaglutide QW, show that when slow dose escalation is implemented, higher doses are achieved and the rates of patients reporting GI disorders can be significantly reduced. In the multiple ascending dose portion of the phase 1 trial in diabetics DPO-101, GI tolerability of OPK-88003 was improved with the use of a titration regimen for 60 mg QW. Thus, it is reasonable to anticipate that a slower dose-escalation regimen will exhibit improved tolerability to nausea and vomiting at dose levels higher than the 50 mg dose administered in the previous phase 2 trial (XNAA). As such, for this trial, a slow dose-titration schedule over 8 weeks will be employed to help mitigate the gastrointestinal AEs.

CCI

#### **1.4.1 Rationale for Dose Selection**

Study DPO-203 will include OPK-88003 target dose of 70 mg administered weekly. Based on data from subjects with T2DM in study XNAA, the 70 mg QW dose is anticipated to produce maximal reduction in fasting glucose and HbA1c and yield a greater weight loss than the 50 mg QW dose from the dose-range finding phase 2 trial.

The 70 mg QW dose level will be administered using a fixed dose escalation schedule over 8 weeks. Plasma levels of OPK-88003 reach steady state over 5 weeks with the accumulation ratio for  $C_{max}$  and area under the curve (AUC) up to 2.6-fold. Thus, it is reasonable to apply slow dose titration with dose escalation every 4 weeks. For the first 4 weeks of dose escalation subjects will receive 20 mg followed by 4 weeks of 40 mg administered QW. Safety and tolerability from the previous phase 2 trial support evaluation of the dose levels planned for the 8-week dose escalation period.

A population PK model with a first order absorption and first order elimination, along with inter-individual variability for all PK parameters was used to simulate the proposed 70 mg QW dose. This dose is 33% higher (for  $C_{max}$  and AUC) when compared to the 50 mg dose that had acceptable safety and tolerability over 24 weeks. Simulated PK exposures derived from XNAA modeling in conjunction with the phase 1 XNAB trial with suprathreshold exposures and nonclinical safety margins support a multiple dose of 70 mg, administered QW, in the targeted population.

OPK-88003 at the target level of 70 mg QW dose at steady state following dose titration (week 30) is predicted to have mean  $C_{max}$  value of 3755 ng/mL and AUC value of 560

$\mu\text{g}\cdot\text{h}/\text{mL}$  based on population PK modeling of the proposed titrated dosing regimen (20 mg/40 mg/70 mg QW). In the clinical pharmacology trial XNAB multiple SC doses of 40 mg administered daily for 7 days resulted in suprathreshold exposures. The geometric mean  $C_{\text{max}}$  of OPK-88003 after 7 days of dosing was 11700 ng/mL with the corresponding AUC of 1789  $\mu\text{g}\cdot\text{h}/\text{mL}$ . The exposures from study XNAB were three-fold higher than the modelled exposures with currently proposed titrated dosing regimen, for both  $C_{\text{max}}$  and AUC. Suprathreshold exposures in XNAB study persisted for approximately three weeks after the last dose due to the long terminal half-life of OPK-88003. The once-a-day dosing regimen resulted in high rates of moderately severe nausea and vomiting that required concomitant medication, however most events resolved within a week after the last dose. The intensity and/or duration of these events is expected to be reduced by a slow dose titration in the current study. In previous OPK-88003 trials, there were no safety concerns reported based on clinical laboratory evaluations and ECGs and no severe or serious AEs (SAEs) at suprathreshold exposures.

The safety data from the human studies confirm dose-related, monitorable AEs related to GI tolerability. Most of the events were single episodes, mild in severity, transient, and self-limited. These events occurred most commonly after the first dose and the incidence then declined to near control levels by the fourth dose, consistent with a GLP-1R agonist effect.

Furthermore, studies of molecules with similar mechanism demonstrate improved tolerability with slow dose titration and longer duration of dosing and have not demonstrated new, unexpected toxicities with longer duration of dosing.

The toxicology program for OPK-88003 provided continuous plasma exposure in rats and monkeys with a BIW dosing schedule and supports the proposed dosing regimen. The safety margins for the 70 mg dose based on the exposures (AUC) derived from population PK modeling in humans and the NOAELs for organ toxicity as determined in rats (3 mg/kg) and monkeys (1.5 mg/kg) after chronic dosing correspond to exposure multiples of 0.7-fold and 10-fold, respectively.

Taking into consideration clinical efficacy and tolerability, QW doses of 70 mg are expected to be tolerated with slow dose-escalation and produce glycemic control and weight loss benefits. The data from this trial together with the data from the previous phase 2 trial will enable robust benefit-risk characterizations in T2DM and will form the basis to assess the effect of dose escalation on OPK-88003 efficacy, safety and tolerability, and support the selection of dose(s) and dose regimen to be included in phase 3 trials.

## **2 STUDY OBJECTIVES**

### **2.1 Primary Objective**

The primary objective of this study is: To evaluate the effect of dose escalation of QW SC OPK-88003 vs placebo injections on HbA1c absolute change from baseline to after 30 weeks treatment in subjects with T2DM inadequately controlled with diet and exercise alone, or treated with a stable dose of metformin.

## 2.2 Secondary Objectives

The secondary objectives of this study are to determine the effect of OPK-88003 vs placebo on:

1. Mean percent (%) body weight change from baseline to after 30 weeks treatment
2. Percent (%) of subjects with 5% or greater body weight loss after 30 weeks treatment
3. Change of FPG from baseline to after 30 weeks treatment
4. Number and percent of subjects achieving HbA1c  $\leq 6.5$

## 2.3 Other Objectives

CCI

3. Percent (%) of subjects permanently discontinued from the study due to hyperglycemia
4. Incidence and rate of gastrointestinal (GI) events, major cardiovascular (CV) events, hypoglycemia, injection site reactions, hypersensitivity reactions and pancreatic events
5. To evaluate immunogenicity of OPK-88003

CCI

## 3 INVESTIGATIONAL PLAN

### 3.1 Overall Study Design and Plan

Study DPO-203 is a randomized, double-blind, dose-escalation, placebo-controlled multicenter phase 2 trial to examine the efficacy and safety of SC OPK-88003 administered

[figure not shown]
at 70 mg QW compared to placebo in subjects with T2DM who have inadequate glycemic control with diet and exercise alone or on a stable dose of metformin.

This trial will be conducted at up to approximately 30 investigational sites in the US. Approximately 200 subjects are expected to be screened and 110 subjects will be randomized to OPK-88003 and placebo in a 1.75:1 ratio.

After randomization, the subjects will follow a fixed dose escalation that includes a dose escalation over 8 weeks. The target dose of 70 mg QW will be reached after receiving 20 mg for 4 weeks followed by 4 weeks of 40 mg QW. A safety review of the 70 mg QW dose level will be performed by the DSMB, after which the target level may be reduced to 60 mg QW. The study duration for individual subjects will be up to 36 weeks. Blinding will be maintained throughout the study.

The design for study DPO-203 is illustrated in [Figure 1](#).

**Figure 1 Study Design for DPO-203**

EOT: end of treatment

↓ indicates dosing

Study procedure timing is outlined in the Schedule of Events ([Appendix 1](#)). Eligibility of subjects will be based on the results of a screening medical history, physical examination, vital signs and clinical laboratory tests. At visit 2, eligible subjects will be randomized (V2), receive training on study drug preparation and injection technique and conduct of routine SMBG, and receive their first dose of study drug. Subjects will return for 11 study visits, **CC** during the 30-week treatment period. A final safety follow-up visit occurs four weeks after the treatment period (V14). Subjects who develop ADA will be asked to return to the clinic approximately four months after the last dose for an additional blood draw.

Throughout the entire study, subjects treated with metformin will remain on the same dose they were receiving at visit 1, unless a temporary increase in dose is needed to treat hyperglycemia (see section 6.11).

CCI

### 3.2 Rationale for Study Design and Control Group

This phase 2 trial is designed to establish the effect of a dose-escalation regimen on safety, tolerability and efficacy of 70 mg QW OPK-88003 in subjects with T2DM, relative to placebo. The study duration, target population and efficacy endpoints are typical of phase 2 trials and are consistent with FDA guidance. A four-week follow-up after the treatment period will ensure an adequate time to assess reversibility of any clinical or laboratory abnormalities. Subjects who develop ADA will have one additional follow-up assessment approximately four months post last dose.

This clinical study will enroll subjects with inadequate glycemic control based on HbA1c values ranging from 7.0% to 10.5%, inclusive. Similar ranges of screening HbA1c have been used in numerous studies of T2DM treatments.

Subjects treated with diet and exercise alone or in combination with stable metformin monotherapy ( $\geq 1000$  mg/day), will be enrolled. Subjects on a second oral anti-hyperglycemic medication (OAM) may also be eligible if the second OAM was discontinued 3 months or more prior to visit 1. Stable metformin treatment for at least 3 months is required to minimize baseline glucose drift prior to study entry.

### 3.3 Study Duration and Dates

The study duration for individual subjects will be up to 36 weeks and will consist of four phases: screening (up to 2 weeks prior to first dose), dose escalation (8 weeks), target dose/maintenance (22 weeks) and follow-up (4 weeks).

The trial is expected to commence recruitment during Q1 2018. Recruitment for this trial is expected to take approximately 5 months.

## 4 STUDY POPULATION

Overweight and obese T2DM subjects treated with diet and exercise alone or on a stable dose of metformin.

---

 Guidance for Industry: Diabetes Mellitus: Developing Drugs and Therapeutic Biologics for Treatment and Prevention. Draft guidance February 2008

#### 4.1 Inclusion Criteria

Subjects are eligible to be included in the study only if they meet all of the following criteria at the indicated visit:

1. Have T2DM for at least 6 months before entering the trial based on the disease diagnostic criteria ([AmDA 2018](#)), controlled with diet and exercise alone or with a stable dose of metformin ( $\geq 1000$  mg/day) for at least 3 months prior to visit 1.
2. Males or females 18 to 80 years of age inclusive.
3. Females must be not of childbearing potential due to surgical sterilization (hysterectomy or bilateral oophorectomy or tubal ligation) or menopause. Women with an intact uterus are deemed postmenopausal if they are  $\geq 45$  years old, and
  - have not taken hormones or oral contraceptives within the last year and had cessation of menses for at least 1 yearOR
  - have had at least 6 months of amenorrhea with follicle-stimulating hormone (FSH) levels consistent with a postmenopausal state (FSH  $\geq 40$  mIU/mL).
4. Have an HbA1c value at screening of  $\geq 7.0\%$  and  $\leq 10.5\%$ .
5. Have a Body Mass Index (BMI)  $\geq 27$  and  $\leq 45$  kg/m^2 at screening.
6. In the investigator's opinion, are capable and willing to:
  - administer weekly study medication injection (with assistance if necessary)
  - complete study diaries
  - follow lifestyle counseling advice
  - perform SMBG
7. Are willing to be available for the duration of the trial, comply with the required study procedures and visits, and abide by the clinical research site policy.
8. Have given written informed consent.

#### 4.2 Exclusion Criteria

Subjects will be excluded if they meet any of the following criteria at visit 1, unless otherwise specified:

1. Participation in any other interventional trial within 30 days.

2. Have Type 1 diabetes mellitus.
3. Previous exposure or known allergies to OPK-88003 or its components.
4. Previous treatment with incretin mimetic drugs (GLP-1 agonists), excluding DPP-IV inhibitors.
5. Have used insulin for diabetic control for more than 6 consecutive days within the prior year.
6. Use of thiazolidinedione, or any other drugs, including investigational drugs, for treatment of hyperglycemia (except metformin), within the prior 3 months.
7. Use of systemic (including nasal and inhaled) glucocorticoids within the prior month, or subjects likely to require systemic doses of glucocorticoids during study participation are also excluded. Topical applications are permitted.
8. Evidence of hepatitis B and/or positive hepatitis B surface antigen. Evidence of hepatitis C.
9. Evidence of human immunodeficiency virus (HIV) and/or positive HIV antibodies.
10. Have cardiac disease with functional status that is NYHA Class III, or IV or in the last 6 months have had any of the following: myocardial infarction (MI), unstable angina, acute coronary syndrome, coronary artery bypass graft (CABG), percutaneous coronary intervention (PCI; diagnostic angiograms are permitted), transient ischemic attack (TIA), cerebrovascular accident (for example, stroke) or decompensated congestive heart failure.
11. Have hypertension (mean systolic blood pressure  $>160$  mm Hg or mean diastolic blood pressure  $>100$  mm Hg), malignant hypertension, renal artery stenosis, and/or evidence of labile blood pressure including symptomatic postural hypotension at visit 1. If on treatment for hypertension, doses of antihypertensive medications must be stable for the prior 30 days.
12. Have obvious clinical signs or symptoms of liver disease, acute or chronic hepatitis, or an alanine transaminase (ALT) or aspartate aminotransferase (AST) levels  $>2.5$  x upper limit of normal (ULN) or serum total bilirubin  $>2.0$  mg/dL.
13. Evidence of hypothyroidism or hyperthyroidism based on clinical evaluation and/or an abnormal thyroid-stimulating hormone (TSH). Subjects on a stable dose of thyroid replacement therapy for at least the prior two months may be eligible if they meet the other criteria.
14. Evidence of obesity induced by other endocrinologic disorders (eg. Cushing Syndrome).
15. Clinically significant peripheral vascular disease in the opinion of the investigator.

16. Active proliferative diabetic retinopathy.
17. Known significant autonomic neuropathy as evidenced by urinary retention, resting tachycardia, orthostatic hypotension or diabetic diarrhea.
18. Have an active or untreated malignancy or have been in remission from a clinically significant malignancy (other than basal or squamous cell skin cancer, in situ carcinomas of the cervix or in situ prostate cancer) for less than five years. Have a personal or family history of thyroid medullary C-cell hyperplasia, focal hyperplasia, carcinoma (including sporadic, familial or part of Multiple Endocrine Neoplasia syndrome type 2A or 2B), or a serum calcitonin  $\geq 20$  pg/mL.
19. Impaired renal function (eGFR  $< 60$  mL/min/1.73 m^2).
20. Triglycerides  $> 600$  mg/dL (6.84 mmol/L) at screening. If subject is on lipid lowering therapies doses must be stable for 30 days prior to screening.
21. Any subject having experienced a keto-acidotic episode requiring hospitalization in the prior 6 months.
22. Have an ECG considered by the investigator indicative of active cardiac disease or with abnormalities that may interfere with the interpretation of changes in ECG intervals. A QTcB interval greater than 450 msec in men and greater than 470 msec in women at visit 1 or visit 2 is specifically excluded.
23. Personal or family history of long QT syndrome, family history of sudden death in a first-degree relative (parents, sibling, or children) before age 40 or personal history of unexplained syncope within the last year. Use of prescription or over-the-counter medications known to prolong the QT or QTc interval.
24. History or presence of CV, respiratory, hepatic, renal, GI, endocrine (other than diabetes), hematological, or neurological disorders capable of significantly altering the absorption, or metabolism or elimination of drugs or of constituting a risk when taking the study medication or interfering with the interpretation of data.
25. Diagnosis of gastroparesis or bariatric surgery prior to screening, or planned bariatric surgery for the trial duration period.
26. Have had more than one episode of severe hypoglycemia within 6 months prior to visit 1, as defined by hypoglycemia associated with severe cognitive impairment requiring external assistance for recovery, or has a history of hypoglycemia unawareness or poor recognition of hypoglycemic symptoms. Any subject that the investigator feels will not be able to communicate an understanding of hypoglycemic symptoms and the appropriate treatment of hypoglycemia should also be excluded.

27. Have had two or more emergency room visits or hospitalizations due to poor glucose control within the prior 6 months.
28. Have taken prescription or over-the-counter medications to promote weight loss within the prior 3 months.
29. Have had a significant change in weight, defined as a gain or loss of more than 5% in the prior 3 months.
30. Are currently taking CNS stimulants (eg, Ritalin-SR®) with the exception of caffeinated beverages.
31. Have had a blood transfusion or severe blood loss within the prior 3 months or have known hemoglobinopathy, hemolytic anemia, sickle cell anemia, or have a hemoglobin value <11 g/dL (males) or <10 g/dL (females), or any other condition known to interfere with HbA1c methodology.
32. Blood donation of 450 mL or more in the prior 3 months or any blood donation within the prior month.
33. Have a history of alcohol or drug dependence or abuse within the last 2 years and/or have an average weekly alcohol intake that exceeds 21 units per week (males) and 14 units per week (females) [1 unit = 12 oz. or 360 mL of beer; 5 oz. or 150 mL of wine; 1.5 oz. or 45 mL of distilled spirits].
34. Have a history of atopy (severe or multiple allergic manifestations) or clinically significant multiple or severe drug allergies, or intolerance to topical corticosteroids, or severe post-treatment hypersensitivity reactions (including, but not limited to, erythema multiforme major, linear IgA dermatosis, toxic epidermal necrolysis, anaphylaxis, angioedema, or exfoliative dermatitis).
35. Have a history of acute or chronic pancreatitis or confirmed elevation in serum lipase/amylase (>2 x ULN).
36. Have any other condition or psychiatric disorder that, in the opinion of the investigator, may preclude the subject from following and completing the protocol related procedures.
37. Are unsuitable for inclusion in the study in the opinion of the investigator or sponsor.
38. Are unable to undergo MRI for any reason **CCI**

## 5 DISCONTINUATIONS

### 5.1 Discontinuation of Study Drug

#### 5.1.1 *Temporary Discontinuation of Study Drug*

After randomization, the investigator may decide to temporarily discontinue study drug, for example, due to an AE or a clinically significant laboratory value. Every effort should be made by the investigator to maintain subjects in the study and to restart study drug promptly as soon as it is safe to do so. The dates of study drug discontinuation and re-start will be documented. If a subject misses more than four doses of study drug throughout the course of the study or two consecutive doses during the dose escalation phase, they should be discontinued from the study (see section 5.2).

Subject noncompliance with study drug regimen should not be recorded as temporary discontinuation of study drug (see section 7.11).

#### 5.1.2 *Permanent Discontinuation of Study Drug*

Permanent discontinuation of the study drug during the dose escalation and maintenance phase should be considered by the investigator, after consultation with the sponsor designated medical monitor, when the subject meets the following conditions:

- Abnormal liver tests:
  - Alanine aminotransferase (ALT) or aspartate aminotransferase (AST) >8 x ULN
  - ALT or AST >5 x ULN for more than 2 weeks
  - ALT or AST >3 x ULN and (total bilirubin level >2 x ULN or INR >1.5)
  - ALT or AST >3 x ULN with the appearance of fatigue, nausea, vomiting, right upper-quadrant pain or tenderness, fever, rash, and/or eosinophilia (>5% compared to baseline)
- AEs:
  - Confirmed pancreatitis or pancreatic cancer (see section 8.3.5)
  - Estimated glomerular filtration (eGFR) <30 mL/min/1.73 m^2
  - Any severe injection site reaction or two or more moderate injection site reactions occurring a week or more apart (see section 8.3.1)
  - Any study drug related systemic hypersensitivity reaction (see section 8.3.2)
  - Any nonfatal major CV events (see section 8.3.6)

- Any SAE or clinically significant event (CSE) judged to be related to study drug. A CSE is defined as a moderate to severe AE, abnormal clinical sign, or clinical laboratory finding that may pose a risk to the wellbeing of the subject. A CSE will be determined by the investigator, and may include findings that do not fulfil the criteria for SAEs ([Appendix 2](#)).
- Any other TEAE, SAE or clinical significant laboratory value for which the investigator believes that permanent study drug discontinuation is the appropriate measure to be taken.
- Serum calcitonin with an absolute value of  $\geq 50$  pg/mL on repeat testing
- The subject intentionally or repeatedly takes more than the prescribed dose of study medication.

Subjects who are permanently discontinued from study drug will be discontinued from the study (see section [5.2](#)).

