#### **7.11 Treatment Compliance**

Treatment compliance will be verified by investigative sites. Subjects will be asked to return all their used and unused cartons with vials to the investigative site for accountability as per schedule of events.

Subjects that miss more than four doses of study drug over the course of the study, or miss two consecutive doses of study drug during the dose escalation phase are considered non-compliant. A subject will also be considered non-compliant if he or she is judged by the investigator to have intentionally or repeatedly taken more than the prescribed amount of study drug. Subjects that are noncompliant will be discontinued from the study (see section 5.2).

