### **8.3.5 Acute Pancreatitis**

Acute pancreatitis (AP) is an acute inflammatory process of the pancreas that may also involve peripancreatic tissues and/or remote organ systems. The diagnosis of AP requires two of the following three features:

- Abdominal pain, characteristic of acute pancreatitis (generally located in the epigastrium and radiates to the back in approximately half of the cases; the pain is often associated with nausea and vomiting)
- Serum amylase and/or lipase  $\geq 3$  x ULN
- Characteristic findings of AP on computed tomography (CT) scan or magnetic resonance imaging (MRI)

If a subject experiences severe or serious abdominal pain or if acute/chronic pancreatitis is suspected, administration of study drug should be temporarily discontinued. If AP is suspected, appropriate laboratory tests (including levels of amylase and lipase) should be obtained. These laboratory tests may be obtained locally but, if possible, a serum lipase and amylase should also be sent to the central laboratory (for capture of data in the clinical trial database) at the time of presentation. If serum amylase and/or lipase values are confirmed  $\geq 3$  x ULN, imaging studies, such as abdominal CT scan with or without contrast, MRI, or abdominal ultrasound, to include pancreas and gallbladder, should be performed. If diagnostic testing does not support the diagnosis of acute or chronic pancreatitis then study drug may be resumed as soon as it is safe to do so in the judgment of the investigator. If diagnostic testing supports the diagnosis of acute or chronic pancreatitis or pancreatic cancer,

the subject must permanently discontinue study drug. A review of the subject's concomitant medications should be conducted to assess any potential causal relationship with pancreatitis.

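### Protocol 5.1.2 asks only that stopping be considered for two events (overdosing and pancreatic disease) where 7.11 and 8.3.5 give stronger instructions

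*Protocol*

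**What the plan says.** Protocol 5.1.2 has one lead-in for its whole list of conditions: permanent discontinuation of study drug "should be considered by the investigator, after consultation with the sponsor designated medical monitor". No item is exempted. Two of the items matter here.

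- **Overdosing.** The 5.1.2 item reads "The subject intentionally or repeatedly takes more than the prescribed dose of study medication" and has no cross-reference. Section 7.11 classes as non-compliant a subject "judged by the investigator to have intentionally or repeatedly taken more than the prescribed amount of study drug", and then says: "Subjects that are noncompliant will be discontinued from the study". It refers to 5.2 for this.
- **Pancreatic disease.** 5.1.2 lists confirmed pancreatitis or pancreatic cancer and cites 8.3.5. Section 8.3.5 says: "If diagnostic testing supports the diagnosis of acute or chronic pancreatitis or pancreatic cancer", then "the subject must permanently discontinue study drug".

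Section 5.2 lists the circumstances in which a subject leaves the study. It names missed doses but not excess doses. It also names permanent discontinuation of study drug, and for that it refers to 5.1.2. The last line of 5.1.2 adds that a permanent drug stop ends study participation. Neither document says which section takes precedence.

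**The concern.** Going by its title, 5.1.2 is where a site would look first when deciding whether a subject may stay on drug. If its wording is weaker than that of the section dealing with the particular event, two sites facing the same event can act differently and each cite the protocol. One considers stopping, consults the medical monitor and continues; the other withdraws the subject.

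The stake is consistent safety handling. Pancreatic events are an adverse event of special interest in this trial, and discontinuations due to adverse events are to be summarised by arm. Both are harder to interpret if the rule behind them varied by site. There could also be an effect on the analysis, because stopping drug means leaving the study and so having no Week 30 HbA1c. The working checks whether that effect is large enough to matter.

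**Working it through.** The protocol gives no figure for this point, so the main check is textual.

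**1. Overdosing.** The 5.1.2 item and the 7.11 definition describe the same conduct. In 5.1.2 the consequence is consideration of a drug stop. In 7.11 the trigger is an investigator judgement, but once that judgement is made the consequence is discontinuation from the study, with no further discretion. Following the references: 7.11 sends the reader to 5.2; 5.2 does not list overdosing; its nearest specific item is a permanent drug stop, which sends the reader to 5.1.2; and 5.1.2 says to consider it. The other items in 5.2 that could apply are general (the investigator's view of the subject's best interests, or a sponsor decision) and are also discretionary. The chain starts with a mandatory instruction and ends with a discretionary one.

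**2. Pancreatic disease.** 5.1.2 speaks of a confirmed diagnosis, 8.3.5 of one that testing supports. A confirmed case can be expected to meet the 8.3.5 wording, so the two are treated here as the same event. A site that follows the reference in 5.1.2 reaches the mandatory text. The lead-in under which the item stands still says only that stopping is to be considered.

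**3. Which outcomes each section allows.**

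| Outcome | 5.1.2 | 7.11 (overdosing) | 8.3.5 (pancreatic disease) |
|---|---|---|---|
| Considered, then stopped and withdrawn | allowed | satisfied | satisfied |
| Considered, then continued | allowed | not allowed | not allowed |

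The first row meets every section. The disagreement lies wholly in the second row.

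**4. Size of any analysis effect.** The documents give no expected rate for either event in this trial. For pancreatic events, Protocol 1.3 reports 11 potential events in 10 subjects, of which one in the OPK-88003 group was adjudicated as an actual pancreatic event. The denominator is not stated. Assume it lies between 280 (the denominator used for injection site reactions in 1.3) and 402 (all subjects who have received OPK-88003, also 1.3):

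- rate: 1/402 = 0.25% to 1/280 = 0.36%;
- expected among 70 active subjects: 70 × 1/402 = 0.17 to 70 × 1/280 = 0.25.

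This is indicative only, because the target dose and the treatment period here exceed those of the earlier phase 2 trial. There is no comparable figure for overdosing.

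Under SAP 5.1 a missing Week 30 HbA1c is imputed only after early discontinuation for hyperglycemia, so such a subject would have no Week 30 value. The primary analysis in SAP 6.9.1 is an MMRM over the scheduled visits, however. A subject with HbA1c at Weeks 4, 8, 12 or 22 still contributes. Withdrawal before Week 26 could remove the subject from the per-protocol set (SAP 6.3.4), but that again concerns very few subjects.

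**The case against.** The strongest answer is that nothing here is contradictory. 5.1.2 does not tell anyone to continue. An investigator who consults the medical monitor and then stops complies with all the sections, and 5.1.2 can be read as a general prompt that the specific sections tighten. This is right as far as it goes. A reader might infer that the sections give opposite orders or cannot both be obeyed, and the documents do not support that. What stands is that 5.1.2 permits an outcome that 7.11 and 8.3.5 do not, and no precedence rule says that the specific section governs.

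Second, the pancreatitis item cites 8.3.5, so a site that reads 5.1.2 in full is directed to the mandatory text. This makes it the weaker of the two examples. It does not help with overdosing, where there is no pointer and the path through 5.2 leads back to the discretionary wording.

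Third, 7.11 requires withdrawal from the study, not a drug stop as such, and its trigger rests on the investigator's judgement. Both are true. But leaving the study ends dosing, and the judgement concerns only whether the conduct occurred, not what follows from it.

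A reader might also extend the point to calcitonin. 5.1.2 lists a repeat value of at least 50 pg/mL, and under 8.6 the DSMB is to recommend removal from treatment when such a value is confirmed. A recommendation is not a mandate on the investigator, so that pair is not counted here.

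**Conclusion.** The point holds as an inconsistency of force between sections that describe the same events. It is clearest for overdosing, where the cross-references fail, and weaker for pancreatic disease, where the cross-reference exists but the lead-in is softer than the text it leads to. It is a matter of safety wording, to be corrected because a stopping rule should read the same wherever a site meets it.

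Few subjects would be affected: an indicative 0.17 to 0.25 pancreatic events among 70 active subjects, on the assumed denominators, and an unknown but presumably small number of overdosing cases. A reader might infer that the choice of section materially affects the primary result because it can decide whether a subject has a Week 30 value. The documents do not support that: the events appear rare, and the MMRM uses the earlier visits. The effect on the Week 30 analysis is negligible.

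The conclusion rests on reading the 5.1.2 lead-in as governing every item beneath it, which is how the text is laid out, and on the absence of any precedence statement in either document.

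**What to change.** Reconcile the four sections:

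- In 5.1.2, mark which items are mandatory and which are discretionary, instead of placing all of them under one lead-in.
- Add the missing cross-reference between the overdosing item in 5.1.2 and 7.11.
- Make 5.2 agree with 7.11, so that the reference from 7.11 leads to an item that covers overdosing.
- Give the pancreatic item in 5.1.2 and the text of 8.3.5 the same trigger and the same force.

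Which instruction applies to each event is for the sponsor's medical team to decide; this review takes no view.

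The cost is protocol wording, in a clarification or the next amendment, with no change to the analysis. SAP 6.1 already describes enrolment in the past tense. If dosing has also finished, what remains is to state in the clinical study report which rule was applied to any subject with either event, and to correct the wording before it is reused in a later protocol.
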